## 5. OBJECTIVES AND ENDPOINTS

### 5.1. Primary Objective and Endpoint

#### 5.1.1. Primary Efficacy Objective

To evaluate whether StrataGraft treatment eliminates or reduces the need for autografting and promotes wound closure in a pediatric population with thermal burns that contain intact dermal elements and for which autografting is clinically indicated (DPT burns).

#### 5.1.2. Primary Efficacy Endpoint

Percentage of subjects achieving confirmed complete closure of StrataGraft treatment sites on or before Week 12 without autograft placement. Confirmed complete wound closure is defined as complete skin re-epithelialization confirmed at 2 consecutive visits at least 2 weeks apart but no later than Week 20.

#### 5.1.3. Primary Outcome Measures:

- Percentage of participants achieving confirmed complete closure of StrataGraft treatment sites without autograft within 12 weeks of StrataGraft application, ie, percentage of participants whose burn healed after StrataGraft treatment without needing the doctor to treat the burn with skin cut from other parts of the patient's own body.
- Number of participants with treatment-emergent adverse events (TEAEs) that occurred between StrataGraft application and the end of the study (within 12 months of last data collection) and considered related to StrataGraft. This measure is not to be considered as a measure of study success.

### 5.2. Secondary Efficacy Endpoints

The secondary efficacy endpoints, in hierarchical order, are:

1. Mean of averaged percent area of StrataGraft treatment sites per subject closed at Week 12 without autograft placement.
2. Number (%) of confirmed complete wound closures of the StrataGraft treatment sites on or before Week 12 without autograft placement.
3. Mean of averaged percent area of StrataGraft treatment sites per subject autografted by Week 12.

### 5.3. Exploratory Endpoints and Assessments

- Mean percent area of StrataGraft treatment site closed without autograft placement at Week 8.
- Mean Patient and Observer Scar Assessment Scale (POSAS) Observer total score at Week 12, and Months 6 and 12.

- Changes in skin quality outcome at StrataGraft treatment site (POSAS and Patient Scar Assessment Questionnaire [PSAQ] scores) across time.
- Incidence and severity of pain at the StrataGraft treatment site using EVENDOL (EVAluation ENfant DOuLeur, ie, Evaluation of Child Pain; observer or parent) or FPRS (6 faces with expressions denoting degrees of pain; subject) rating scales over time.
- Percent of subjects with complete closure of StrataGraft treatment site without autografting at Weeks 6 and 12, and Months 6 and 12.
- Time to complete closure following application of StrataGraft.
- Mean percent wound closure of treated wound area over time from Day 21 through Month 12.
- Percent of subjects achieving and maintaining persistent wound closure at Months 6 and 12.
- Mean scar satisfaction based on PSAQ scores at Week 12, and Months 6 and 12.

#### **5.4. Safety Endpoints and Assessments**

The assessment of safety of StrataGraft in pediatric subjects.

Acceptable safety profile at Week 12 and Month 12, as determined by the Data Safety & Monitoring Committee (DMC; Section 13.6), with regard to:

- TEAEs.
- Serious adverse events (SAEs).
- Vital signs.
- Wound-related adverse events, including infection, throughout the study duration.
- Safety laboratory values (complete blood count with differential and comprehensive metabolic panel).
- Where practical, panel reactive antibodies (PRA) and anti-bovine serum albumin (BSA) antibodies.

## 6. INVESTIGATIONAL PLAN

### 6.1. Overall Study Design

This is a prospective, open-label, single arm study to examine the safety, tolerability and clinical efficacy of StrataGraft in the treatment of DPT thermal burns in pediatric subjects. The study population will include pediatric subjects ages 2 to 17 years, inclusive, with thermal burns that contain intact dermal elements and for which autografting would be part of standard of care. As previously discussed, far more pre-school and school-aged children are burned than adolescents. Qualified subjects will be enrolled into one of two age-based cohorts: 2 to < 12 years (up to n=40) and 12 to  $\leq$  17 years (up to n=10).

Informed consent will be obtained from parents/guardians and assent from the child, when appropriate, as determined by the IRB and consistent with regulatory criteria and requirements before any protocol-related assessments or procedures are conducted. After consent is provided, data collected during the course of admission and routine assessment may be abstracted from the medical record and used for study purposes.

Following a screening period of up to 14 days, subjects will be enrolled and receive a single application of StrataGraft to 0.5% to 10% total body surface area (TBSA), which may be composed of up to 3 non-contiguous areas located on the same extremity or plane of the torso.

Subjects will return to for weekly visits until complete wound closure of all study treatment sites is confirmed. Follow-up visits will be conducted at Week 12 and Months 6 and 12. Subjects will participate in the study for approximately 13 months, not including the screening period of up to 14 days. The Schedule of Study Events is provided in [Table 2](#).

The duration of the study from first subject first visit to last subject last visit will depend upon the ability of the sites to identify and enroll eligible subjects. The study is expected to enroll subjects over a period of 12 to 18 months. The entire study is expected to require approximately 2.5 years to complete.

Safety assessments will include monitoring incidence of AEs, wound-related events, vital signs, clinical laboratory values (where possible), immunological markers (where possible), wound closure, pain, and scarring.

Subjects will undergo baseline assessments including a targeted physical examination and collection of clinical laboratory assessments during Screening. After enrollment and StrataGraft application, wound assessments, photographs, and solicitation of AEs will be performed at each study visit via telephone or video interaction if the subject is unable to attend the visit. However, wound closure may only be assessed at face-to-face visits. If not collected during Screening, clinical laboratory samples will be collected via venipuncture performed prior to StrataGraft application on Day 1. Immunological samples (monitoring of PRA and anti-BSA antibodies) will be collected prior to StrataGraft application, and again between Week 6 and Month 6 for all treated subjects.

A subject's study participation ends after the Month 12 visit. However, during the study period, should a subject return to the investigator for a follow-up visit not scheduled for the purposes of the study, the investigator, when feasible, will record any update on the subject's wound status

and safety information and report such information to the Sponsor using the data collection forms provided for such an Unscheduled visit.

## **6.2. Study Design Rationale**

Deep partial thickness and full thickness burns that are expected to take longer than 3 weeks to heal are usually autografted, as this reduces the incidence of hypertrophic scarring and results in better cosmesis (Heimbach, 1987; Chipp, 2017). Donor sites are painful and patients have remarked that they are more painful than the burn injury itself (Romanelli, 2019; Sinha, 2017). Availability of autologous donor tissue is limited by the extent of the burn injury, and in larger injuries, donor sites may be repeatedly harvested, increasing the likelihood of scarring at those sites.

Clinical data from the STRATA2016 pivotal study of StrataGraft use for promoting the closure of DPT thermal burns in adult subjects demonstrated that more than 95% of subjects achieved closure without autografting after treatment with StrataGraft, thereby obviating the harvest of autograft and the pain associated with donor sites.

## **6.3. Treatment Rationale**

StrataGraft is a viable, bioengineered, allogeneic, cellularized scaffold product that is anticipated to provide immediate wound coverage, aid in wound bed conditioning, and promote autologous tissue regeneration and wound closure while reducing or eliminating the need to harvest autologous donor tissue in adults.

Recent clinical data in adults demonstrate that treatment of DPT thermal burns with StrataGraft results in wound closure while reducing or eliminating the need for autograft. Although similar to the pivotal study in adults (ie, STRATA2016), this study of pediatric subjects will recruit not only younger subjects (ie, not adults) but also subjects with smaller TBSA burn. The reduced TBSA burn in pediatric subjects reflects the greater surface area to mass ratio of children compared to adults and the accompanying fluid status lability, limited physiologic reserves, as well as the reduced body size and attendant challenges.

The present study is being conducted to explore the efficacy and safety of StrataGraft in pediatric subjects with thermal burns containing dermal elements to better understand the product profile in a pediatric population.

## **6.4. Study Stopping Rules**

In this study, the medical monitor as well as the DMC will assess safety and efficacy. The DMC will be independent of study conduct and their activities governed by a Charter.

Subject enrollment may be paused pending discussion with the DMC if any of the following events occur:

- Unexpected infection at the StrataGraft treated site that is possibly or probably related to StrataGraft and is an SAE.
- Severe acute hypersensitivity reaction attributed to StrataGraft.
- Death attributed to StrataGraft.

In the event that one or more of the above occurs, the Sponsor will be notified, per timelines in Section 11.12. The medical monitor will review the safety data associated with the adverse reaction with the clinical investigator and generate a summary narrative. The medical monitor and DMC will conduct a comprehensive review of the safety data, prior to resumption of subject enrollment.

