##### **Life-threatening**

An adverse event or suspected adverse reaction is considered "life-threatening if, in the view of either the investigator or Sponsor, its occurrence places the subject at immediate risk of death. It does not include an AE or suspected adverse reaction that, had it occurred in a more severe form, might have caused death. For example, hepatitis that resolved without evidence of hepatic failure would not be considered life-threatening, even though hepatitis of a more severe nature can be fatal. Similarly, an allergic reaction resulting in angioedema of the face would not be life-threatening, even though angioedema of the larynx, allergic bronchospasm, or anaphylaxis can be fatal.

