#### **11.9.1.5. Adverse Event of Special Interest**

An adverse event of special interest (serious or nonserious) is one of scientific and medical concern specific to the sponsor's product or program, for which ongoing monitoring and rapid communication by the investigator to the sponsor can be appropriate. AESI will be reported using the SAE/AESI Report Form and observe the same reporting timeline ([Table 6](#)). For this study, Adverse Events of Special Interest (AESI) include:

- Signs/symptoms of endotoxin reaction (ie., combination of hypo/hyperpyrexia, hypo/hypertension, tachycardia, tachypnea, and change in mental status) within 24 hours after StrataGraft application
- Unexpected or unusual infections
- Dermatological malignancy

If any of the above occurs, the event will be reported within 24 hours of first knowledge of the event and follow-up reports provided as changes in the event occur. Photographs will be taken of the affected wound(s) to document the AESI.

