## 11.11. Severity Assessment

For purposes of consistency, if required the investigator may use the intensity grades presented in [Table 5](#).

**Table 5:** Adverse Event Intensity Grades

Grade	Definition
Mild	Does not interfere with subject's usual function and activities.
Moderate	Interferes to some extent with subject's usual function and activities.
Severe	Interferes significantly with subject's usual function and activities.

To ensure there is no confusion or misunderstanding of the difference between the terms “serious” and “severe,” which are not synonymous, the following note of clarification is provided:

The term “severe” is used to describe the intensity of a specific event (as in mild, moderate, or severe myocardial infarction). The event itself, however, may be of relatively minor medical importance (such as a severe headache). This is not the same as “serious,” which is based on the subject/event outcome or action criteria usually associated with events that pose a threat to a subject’s life or functioning. Seriousness (not severity) serves as a guide for defining regulatory reporting obligations.

If an AE increases in severity (eg, from moderate to severe); decreases in severity (eg, changes from moderate to mild); or if there is a change in seriousness, a new AE will be opened and the original AE will be closed. If an AE is still ongoing at the time of a subject’s completion of the last study follow-up visit, the resolution/stop date and time is left blank.

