**Table 6: Reporting Requirements for Adverse Events**

Category	Reporting Time	Type of Report
Serious adverse events, and AESIs	Within 24 hours of first knowledge of event	Initial report on the SAE/AESI Form, appropriate eCRF, and source document
	Within 24 hours of receipt of follow-up information	Follow up report on the Follow-up SAE/AESI Form, appropriate eCRF, and source document
Nonserious adverse events	Per case report form submission procedure	Appropriate eCRF and source document

AESI = adverse event of special interest; eCRF = electronic case report form; SAE = serious adverse event.

It is **not** acceptable for the investigator to send photocopies of the participant's medical records to the Sponsor in lieu of completion of the SAE report form.

There may be instances when copies of medical records for certain cases are requested by the Sponsor. In this case, all participant identifiers, with the exception of the participant number, will be redacted on the copies of the medical records before submission to an agency.

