### **13.8. Data Quality Assurance**

The Sponsor performs quality control and assurance checks on all clinical studies that it financially supports. Before enrolling any subjects in this study, Sponsor personnel and the investigator review the protocol, the investigator's Brochure, the eCRF and instructions for their completion, the procedure for obtaining informed consent, and the procedure for reporting AEs and SAEs. A qualified representative of the Sponsor will monitor the conduct of the study.

The investigator will permit study-related monitoring, audits, IRB/IEC review, and regulatory inspections by providing direct access to original source data and documents.

Each subject's eCRF should be fully completed in a timely fashion, usually within 5 business days.

If an investigator retires, relocates, or otherwise withdraws from conducting the study, the investigator must notify the Sponsor to agree upon an acceptable storage solution. Regulatory agencies will be notified with the appropriate documentation.

Any changes in investigator(s) or sub-investigator(s) will be promptly disclosed to the Sponsor and will require an updated Statement of Investigator (ie, FDA form 1572). As such, the investigator must promptly disclose these changes to the Sponsor or their designee.

The investigator must notify their IRB/IEC of protocol deviations in accordance with local regulatory and IRB/IEC requirements.

The eCRF data are stored in a database and processed electronically. The Sponsor's medical monitor will review the data for safety information. The data are also reviewed for completeness and logical consistency. Automated validation programs will identify missing data, out-of-range data, and other data inconsistencies. In addition, clinical laboratory data will be processed electronically. Requests for data clarification will be forwarded to the study site for resolution and responded to in a timely fashion, usually within 5 business days.

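### One of the three enrolment-pause criteria, severe acute hypersensitivity, is not guaranteed 24-hour reporting to the sponsor

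*Combined protocol and SAP*

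**What the plan says.** Protocol Section 6.4 opens its list with a permissive rule: "Subject enrollment may be paused pending discussion with the DMC if any of the following events occur". The three events are an unexpected, related infection at the treated site that is also an SAE; "Severe acute hypersensitivity reaction attributed to StrataGraft"; and a death attributed to the product. The section sets no reporting time of its own. It says that "the Sponsor will be notified, per timelines in Section 11.12".

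Section 11.12 (Table 6) has two routes. SAEs and AESIs are reported within 24 hours of the site learning of the event. Nonserious adverse events are reported "Per case report form submission procedure". There is no separate line for events that meet a pause criterion.

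The AESI list in Section 11.9.1.5 has three items: signs of an endotoxin reaction in the first 24 hours after application, "Unexpected or unusual infections", and dermatological malignancy.

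Section 11.11 separates severe from serious and states: "Seriousness (not severity) serves as a guide for defining regulatory reporting obligations". Table 5 grades an event as severe by how far it interferes with the subject's usual function.

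On eCRF timing, Section 13.8 says that each subject's form "should be fully completed in a timely fashion, usually within 5 business days".

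**The concern.** A pause criterion protects the next child only if the sponsor hears of the event quickly. With about 10 sites planned, other sites can go on treating until the sponsor knows. Section 6.6 adds that withdrawing an applied construct may not be feasible, so much of the protective value of the rule lies with children not yet treated.

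Two of the three criteria are tied to seriousness and so to the fast route. The third is tied to severity, which the protocol itself says does not determine reporting duties. Whether a severe hypersensitivity reaction reaches the sponsor in a day or by routine data entry then depends on whether it also meets a seriousness criterion, and one of those criteria rests on medical judgment.

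There is a smaller wording mismatch. The infection criterion uses the two related classes of Table 4. The hypersensitivity and death criteria speak of attribution, which is not a Table 4 class, so the standing of a possibly related case is not defined.

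**Working it through.** The plan states no figure on this point, so there is none to reproduce. The check is a trace of routes, followed by an illustration of delay.

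**Step 1: trace each Section 6.4 criterion through the reporting rules.**

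| Criterion | SAE by definition? | On AESI list? | Table 6 route |
|---|---|---|---|
| Infection at treated site | Yes, required by Section 6.4 | Infections are listed | 24 hours |
| Death | Yes, Section 11.9.1.4 | Not needed | 24 hours |
| Severe hypersensitivity, serious | Yes, in that case | No | 24 hours |
| Severe hypersensitivity, not serious | No | No, unless it resembles the endotoxin item | Routine eCRF |

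Only the last row lacks a 24-hour duty.

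**Step 2: accrual rate.** Inputs: about 50 subjects (Synopsis) enrolled over 12 to 18 months (Section 6.1). Assumptions: constant rate and Poisson arrivals.

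- 12 months: 50 / 365.25 days = 0.137 per day (4.17 per month)
- 18 months: 50 / 547.9 days = 0.091 per day (2.78 per month)

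**Step 3: further children treated before the sponsor knows.** Expected number = rate × days. Chance of at least one = 1 − exp(−rate × days). I take 5 business days as 7 calendar days. I also assume that the Section 13.8 eCRF target governs the Table 6 route, which gives no number itself.

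| Delay | Expected, 18 to 12 months | Chance of at least one |
|---|---|---|
| 1 day | 0.09 to 0.14 | 9% to 13% |
| 7 days | 0.64 to 0.96 | 47% to 62% |
| 14 days | 1.28 to 1.92 | 72% to 85% |

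For example, at 7 days and 12-month accrual: 0.137 × 7 = 0.958, and 1 − exp(−0.958) = 0.616. The 14-day row shows how the result moves if the soft 5-day target is missed.

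**The case against.** The strongest reply is that very few reactions would fall in the gap. A new reaction that prolongs an existing hospital stay is an SAE under Section 11.9.1.4, and the exclusions listed there do not remove it. The important-medical-event criterion covers reactions that need intervention to avert a serious outcome, and it names bronchospasm treated intensively. A systemic reaction soon after application may show the signs of the endotoxin AESI. This stands and makes the gap narrow. It does not close it: nothing in the protocol makes every severe acute hypersensitivity reaction serious.

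A reader might infer from Section 11.9.1.4 that the protocol supplies its own case in the gap, since "an allergic reaction resulting in angioedema of the face would not be life-threatening". That passage rules out one seriousness criterion only. The same event could be serious through a prolonged stay or medical judgment, so it is not a documented example of a nonserious case.

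A reader might also infer that the reaction triggers a pause automatically. It does not: Section 6.4 allows a pause and does not require one. Late notice still delays the decision.

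On delay, a site could telephone at once, and the DMC Charter, which is not among the documents, may hold further arrangements. Both are possible. Neither is required by the text available.

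On causality, the reply is that attribution naturally means either related class of Table 4. That is a fair reading. It would be speculation to say that a possibly related case would be passed over; the documents support only that the terms differ.

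**Conclusion.** The inconsistency holds on the text. Hypersensitivity is the only pause criterion in Section 6.4 that can be met without a 24-hour reporting duty. The affected cases are those that meet no SAE criterion and do not resemble the endotoxin AESI.

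The 47% to 62% should not be read as the chance that a child in this trial would be treated because of late notice. It is conditional on such an event occurring, on a delay of about 7 days inferred from a general eCRF target, and on Poisson accrual at the planned rate. It stops at the sponsor's awareness and leaves out the time to decide on and carry out a pause. The documents give no rate for the event. Section 4.3 says that no acute immune response has been reported in adults, so the unconditional risk is lower by an amount that cannot be calculated from the documents.

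Severity is minor to moderate. The pause is discretionary, the gap is narrow, and the SAP memo records that enrolment closed in January 2024 with one subject, so no later enrolment remains for the rule to protect. The point matters mainly if this protocol text is reused.

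**What to change.** Reconcile Sections 6.4, 11.9.1.5 and Table 6 so that every pause criterion carries 24-hour reporting, whether or not the event is serious. One way is to add severe acute hypersensitivity reaction to the AESI list; Table 6 then applies without further change. The cost is one line in the protocol, a matching entry on the SAE/AESI form, and an occasional extra expedited report.

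Separately, reconcile the attribution wording in Section 6.4 with the Table 4 classes already used for the infection criterion, so that sites know which causality assessments count. Which threshold applies to hypersensitivity and to death is for the sponsor to decide. This costs a wording change only.
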